**Community Referral Sources** 

- Banyan Health Systems
- Regis House

## 14) Withdrawal of Subjects\*

Participants will be told that this study is completely voluntary and that they have the right not to participate in any intervention procedure. They can also completely withdraw from the study at any time without any negative consequences.

Participants will be told that their participation in the study may be stopped at any time by the investigator of the sponsor without their permission. Possible reasons for removal may include: 1) adolescent is at particular risk for self-harm and more intensive services are needed or 2) adolescent is not attending treatment sessions and may be at risks for self-harm and/or other risky behaviors.

## 15) **Risks to Subjects\***

No side effects have been noted in the current literature in association with the behavioral questionnaires, interviews, or assessments used in this study, although, as with many assessment batteries, some people may experience mild fatigue or momentary concern about their ability to do well. There is some risk in this type of study because of the higher than average incidence of high risk behaviors, such as self-harm that may require that we report some information to outside agencies. All of the steps that may be taken to protect the well-being of family members deemed to be in danger will be described fully to all participants and we will do everything possible to minimize harm to the youth, family or any of its members. The Principal Investigator has conducted six treatment development randomized trials with high risk adolescent populations, including one with adolescents meeting DSM IV criteria for Borderline Personality Disorder, and is highly experienced in working with youth and ensuring their protection from any undue risks.

## 16) **Potential Benefits to Subjects\***

There may be direct benefits to participating in this study. The most important benefit from participation in this study will accrue to adolescents who decrease their self-harm behaviors and risky sexual behaviors and improve their psychosocial functioning and family functioning. Families will also receive a total of \$175 if they complete all assessments.

# 17) Vulnerable Populations\*

Children ages 11-18 will participate in this research study, which meets the additional regulatory requirements described in the HHS regulations, Subpart D. The study protocol, assessments, and consent/assent forms will be submitted to the UM IRB for review and approval. All children (11-17) who agree to participate in the study will sign IRB approved study assent forms. Youth who are 18 years old will sign study participant consent forms. Parent/caregivers will be required to give permission for their child to participate in the study.

The purpose of the research is to build on the Computer Assisted CIFFTA intervention by creating a web-site and web-based delivery system and by adding content that is relevant for the factors that maintain self-harm in Latina adolescents (e.g., depression, family conflict, substance use, and emotion dysregulation) and for unique stressors often linked to sexual/gender minority youth. Selecting youth in middle school and high school (11-18) is justified given the nature of the study and specific research questions to be addressed. CIFFTA was designed and developed for youth in this age range and their families.

The Principal Investigator has conducted six NIH funded trials focused on developing and testing a treatment intervention for high-risk minority youth and their families and has expertise in working with youth. The Project Coordinator/Clinical Supervisor has been Co-principal Investigator and Investigator on these studies and possesses much experience in working with youth and their families. The entire sample will be comprised of youth and their families therefore there will be sufficient youth for meaningful analyses and results to be derived from the study.

## 18) Multi-Site Research\*

NA. This is not a multi-site research study.

## 19) Community-Based Participatory Research\*

NA. This study is not considered community-based participatory research.

## 20) Sharing of Results with Subjects\*

NA. Participants' improved and symptoms will be discussed as part of the clinical process; however, we will not be sharing individual-level scores (e.g., test results, scores). Overall study results will only be shared with participants who express an interest.

## 21) Setting

Study personnel will identify and recruit participants from the main recruitment sites, Banyan Health Systems Mobile Crisis Unit, Mailman Center Adolescent Clinic at the University of Miami Medical Campus, ConnectFamilias, the YES Institute, Regis House, Larkin Hospital, the Institute for Individual and Family

Counseling within our School of Education and Human Development, and the Miami-Dade County Public School System which has special programs for LGBT youth will be utilized.

For the CIFFTA condition, treatment and assessment will take place at the Institute for Individual and Family Counseling or virtually via HIPAA compliant Zoom. For the TAU condition, all study assessment procedures will take place at the IIFC or virtually via HIPAA compliant Zoom and individuals in this condition will receive treatment from treatment agencies in the community either in person or virtually via Telehealth.

### • Therapist(s)

Therapist(s) will be Masters-level counselors that have experience with adolescents and families and that have expertise in working with diverse families. The therapist will be a Spanish speaker able to provide the intervention in Spanish. The therapist will be trained in CIFFTA and will be capable of providing all interventions within a tailored framework. The therapist(s) will be supervised by [name].

### **Other Resources:**

### • Banyan Health Systems Mobile Crisis Unit

Banyan has been operating a 24-hour mobile crisis response team (MCT) for the past decade. The MCT responds to an average of 80 calls per month where approximately 20% are for teens and the vast majority is Hispanic. The unit functions as an outreach service which provides evaluation and crisis intervention. Following an in-depth evaluation in which current mental health and/or substance abuse issues are assessed, the MCT assists in determining which community services are most appropriate based on need, location and family preference. If additional referrals are needed, long-time UM partners such as the Mailman Center Adolescent Clinic at University of Miami Medical Campus, ConnectFamilias, the YES Institute, Regis House, the Institute for Individual and Family Counseling within our School of Education and Human Development, and the Miami-Dade County Public School System which has special programs for LGBT youth will be utilized.

• Nicklaus Children's Hospital Inpatient Psychiatry Department-[name].

## 23) **Prior Approvals**

This study was approved by the IRB on 09/01/2017 for an NIH "Just in Time" request.

## 24) **Recruitment Methods**

The research team has considerable experience in running trials with high riskyouth who are Hispanic. The main recruitment sites will be Nicklaus Children's Hospital and Banyan Health Systems Mobile Crisis Unit. If additional referrals are needed, community agencies with a long-time research partnership with the applicant such as, the Mailman Center Adolescent Clinic at University of Miami Medical Campus, ConnectFamilias, the YES Institute, Regis House, the Institute for Individual and Family Counseling within our School of Education and Human Development, and the Miami-Dade County Public School System which has special programs for LGBT youth will be utilized.

Staff at the referral sites will be trained to identify youth appropriate with this study and in line with the inclusion criteria stated above. They will explain the study to any adolescent and family interested in hearing about it. Staff will then ask families that are interested to sign a release of information to be contacted by

the research study assessor or the family and Crisis Unit staff may contract our staff together. The assessor will be Bachelor's/Master's level research assistant who is bilingual in English and Spanish and will administer all informed consents, assents, and assessments. The assessor will contact the family's that gave permission and explain the study in more detail to them. If the family is interested in participating an appointment for the adolescent and family to come in and hear more about the study will be set up. If they continue to be interested, they will sign an informed consent and assent, in their preferred language that allows the screening of inclusion/exclusion criteria to be made. After the screening has been conducted, the families that do not meet inclusion/exclusion criteria for the study will receive a referral to an appropriate treatment program via warm-handoff procedure.

Materials used for the recruitment of participants (e.g., flyer) have been uploaded for review.

## 25) Local Number of Subjects

A total of 100 youth will be accrued locally. The participants' families will also be included in the study.

## 26) Confidentiality

The issues surrounding confidentiality are of supreme importance and sensitivity because highly personal clinical information will be obtained from the adolescent and their family members. Participants will sign a statement attesting to their understanding that the information they provide will be held as personal and confidential to the extent permitted by law. Consent and assent forms (described above) will clearly state the right to refuse participation at any time. Further, the refusal to participate will not influence any of the services the adolescent or his/her family may receive. In addition to the confidentiality assurances, the participants in the study are protected by a Certificate of Confidentiality under section 301(d) of the Public Health Service Act (42 U.S.C. 241(d), authority delegated to the National Institutes of Health (NIH).

Regarding data/records confidentiality, the UM School of Education and Human Development has an established set of procedures designed to ensure the protection of confidentiality. All project staff will be specifically trained on issues of confidentiality. Due to the use of the web-based REDCap system there will not be any hard copies of the assessment data of the participants. Passwords are used to restrict entry into the REDCap database. There will be very few documents with identifying information (consent forms) and all documents with identifying information will be stored at the UM School of Education and Human Development in locked file cabinets within a locked office. Videotapes, which represent very sensitive clinical material, will also be stored in Box, a secure, HIPAA compliant data storage system maintained by the University of Miami. Use of the videotapes is restricted to the UM School of Education and Human Development and IRB and PI approved research study staff. It should be noted that in our years of clinical research (over 35 years), not a single incident of violation of confidentiality has occurred.

The technology system that will be used in the study will collect usage data that will be securely housed on the project servers. Data will be collected without requiring that the participant actively send them. Interaction and usage information is automatically delivered to the counselor's cellular phones via an existing secure server housed at the University Data Center. Data collected in real-time do not contain names or identifying information, only case numbers. In addition, the system will require a password to see messages sent to the participant. Physical access to servers at the Data Center are controlled by security systems, intruder alarms, and monitored by the Department of Security video surveillance/recording systems. The Data Center provides appropriate environmental control via HVAC systems, uninterruptible Power Supply and emergency generators to maintain power without interruption, and FM200 and Inergen fire suppression systems to extinguish fires without damaging equipment or backup tape systems. The Data Center also provides secure backup for all data systems.

## 27) **Provisions to Protect the Privacy Interests of Subjects**

During the recruitment and consent/assent process, and prior to any data collection, participants will be assured that their information is confidential, and will only be accessed by study staff members. As described above, participants will sign a statement attesting to their understanding that their information will be kept private and confidential to the extent permitted by law. Participants know that they will be assigned unique case numbers (and that their names will not be used) to protect their identity. Participants will be encouraged to ask questions throughout the consent/assent processes and will be provided contact information for both the Principal Investigator ([name]) and the University of Miami's Human Subjects Research Office.

## 28) Compensation for Research-Related Injury

NA.

## 29) Economic Burden to Subjects

NA. Participants may incur costs associated with transportation to and from intervention sessions.

## 30) Consent Process

For those families that meet the inclusion/exclusion criteria and are interested in participating in the research study, the study assessor will obtain a second assent

from the adolescent and informed consent from her/his primary caregiver to participate in the randomized trial. The assessor will provide the adolescent and family members with a copy of the consent and assent forms in person or via Zoom with the screen share option, and, because subjects may have a low level of literacy, will then read the consent and assent forms out loud. Consent and assent forms will also be emailed to the family. The study assessor will explain to the adolescent and her/his family the purpose and procedures of the study. All of their family members will be asked if they are willing to participate in this study. Adolescents and caregivers will be asked if they are willing to be randomly assigned into one of two treatment conditions: CA CIFFTA or TAU. The assessor will explain that they have no way of predicting which family will receive which kind of treatment because this is established by chance (as if by the flip of a coin). If the family decides to participate, they will get paid \$75 at T2 and \$100 at T3. The nature of the confidentiality that surrounds research studies will be discussed with the adolescent and family members, explaining that confidentiality is assured to the extent allowed by law. Specifically, that the information they provide is strictly confidential, except for the case of potential abuse of a child, or danger to their own lives or that of others. The adolescent and family members will be informed that information collected from the research instruments will be used only for research purposes and reported in aggregate form and composite case studies (a strategy for creating case studies in which several cases are integrated into a single case study and all identifiers are removed, to protect confidentiality). They will also be informed that therapy sessions will be videotaped, and they will be asked to provide permission for videotaping sessions for supervision, research, and training. Consent and assent forms clearly specify that any family member has the right to request that their videotapes, and corresponding transcripts be erased/destroyed in part, or in whole at any time during the course of the study or thereafter. In addition, informed consent and assent will be obtained allowing research study staff to call three persons who are close to the adolescent and family members for the purpose of contacting families that may be unreachable at any of the assessment time points.

Once the entire consent and assent form has been read and explained, the assessor will give the adolescent and family members a chance to ask any additional questions. If the family agrees to participate, they will be asked to sign the informed consent and assent forms and will be given copies of each signed form. Youth and families engaging in the consent process via HIPAA compliant Zoom will sign the consent and assent forms with DocuSign. If they do not want to participate, the referral procedure listed above for screen failures will be followed. After the adolescent and family sign the consent and assent forms the assessor will establish a convenient date and time for conducting the baseline assessment (T1). Although most assessments will be completed at the office, some may be done in the participant's home to facilitate data collection. The entire consent and assent process, will be documented by the assessor in the form of a study contact note.

The consent and assent forms for participation in the study and for videotaping family therapy sessions are submitted within this protocol for approval to the University of Miami Institutional Review Board (IRB) Behavioral Subcommittee for the Protection of Human Subjects-

*Non-English speaking participants* will be provided with consent and assent in Spanish. Consent forms have been translated and back-translated by study personnel.

### Waiver or Alteration of Consent Process – NA.

*Subjects who are not yet adults*, which include adolescents ages 11-18 in the current study will go through a similar process for as their parents/family (explained above). After the parent or guardian has consented, study personnel will provide the assent form to the adolescent.

Cognitively Impaired Adults – NA.

Adults Unable to Consent – NA.

# 31) **Process to Document Consent in Writing**

We will be following the "SOP: Written Document of Consent (HRP-091)." Consent and assent forms have been uploaded for review.

### 32) **Drugs or Devices**

NA.

NCT03709472

Computer Assisted Family Intervention to Treat Self-Harm Disparities in Latinas and Sexual/Gender Minority Youth

Statistical Analysis Plan 8/21/24

Data were analyzed using SPSS Version 29 (IBM, 2023). We began our analyses by documenting the number of session and hours of treatment to assess CIFFTA's feasibility and acceptability. We conducted logistic regressions to examine whether baseline characteristics predicted those participants who successfully reached termination and T2 assessments. To examine whether changes in adolescent symptoms of depression over time differed by treatment, a mixed ANOVA was used with depression scores as the within-subjects variable and treatment condition as the between-subjects variable. We used the same analytic strategy to determine whether changes in emotion regulation and family connectedness differed over time by treatment. A series of mixed ANOVAs were used with the Total scores from the PHQ-9, the Difficulty with Emotion Regulation Scale and the Family Connectedness Scale as the within-subjects variables and treatment condition as the between-subjects variable. When effect sizes are reported, cutoffs for partial eta-squared effect sizes are small .01, moderate .06, large .14. Additionally, Chi-Square Tests of Association were used to determine whether the proportion of youth endorsing whether they could talk to their parent about problems differed over time. This analysis was conducted by condition examining mothers and fathers separately.

A complementary analytic strategy was used to investigate change in youth who entered the study with presenting problems in the clinical range at baseline assessments based on established clinical cutoffs (i e., those with at least mild levels of depression at baseline). Descriptive statistics were used to determine the rates of suicidal thoughts and self-harm at baseline and termination by condition. In addition, Chi-Square Tests of Association were used to determine whether the proportion of youth endorsing thoughts of suicide differed by treatment condition.

We also used the Reliable Change Index (RCI) to determine whether the magnitude of change was statistically reliable rather than due to random fluctuations caused by measurement error (Jacobson & Traux, 1991). We examined symptoms of depression.

Lastly, to examine whether changes on the plausible mechanisms of action was associated with the likelihood of engaging in self-harm in the past month at termination in the full sample; after controlling for gender and LGBTQ status, a series of hierarchical logistic regressions were performed. With only two timepoints we could not conduct formal analyses of mediation, but we could explore whether the patterns of change were consistent with plausible mediators. In these models, self-harm in the past month was the binary outcome variable, LGBTQ status and gender were entered in Step 1 as covariates, and the proposed mechanism of action (i.e., depression, parent communication, family connectedness, and emotion regulation) were entered in Step 2.

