Adaptations for youth who report being LGBTQ and/or exposed to trauma, and families. CIFFTA's design lends itself to adaption to diverse populations. Its logic and emphasis on tailoring facilitates the treatment's extension to new populations with unique stressors. During the development phase of this study (first 7 months) we will build on existing modules. Some of the expected adaptations will focus on modules for kids on how they can cope with stressors related to LGBT-related rejection and alienation, emotion regulation and distress tolerance for ameliorating self-harm behaviors, using evidencebased coping strategies for risk factors result from exposure to traumatic events (see Seeking Safety strategies). A module for parents who are having a hard time accepting their son's/daughters being a gender/sexual minority youth will help them to understand the normative stages some parents must go through, allow parents to express their concerns, distress, and fears, so that they are more ready to have a productive family therapy session with their sons and daughters. A parallel module may be offered to youth to increase their readiness to have a family session in which a loving and caring relationship can be created.

Measures: Measures have been selected for: 1) Screening; 2) Ultimate Adolescent Outcomes, e.g., Self-harm; 3) Immediate Outcomes, e.g., depression, emotion regulation, family conflict, and substance use; 4) Cultural Factors; and 5) Additional Measures, e.g., trauma, minority stress. Measures will be administered at Screening, Baseline (T1) 4 months after baseline (Termination or T2), and 12 months after baseline (T3). Spanish versions of the measures are available. Every effort has been made to reduce participant burden. The total battery is expected to take 90 minutes to administer to youth and 40 minutes to parents. These will be administered in person or via HIPAA compliant Zoom. Measures are attached.

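### No pre-specified analysis plan is shown: the only SAP reports finished analyses, names no decisive test or error control, and tests an unlisted outcome between arms while self-harm, the primary endpoint, is only described

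*SAP*

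**What the plan says.** The SAP is headed "Statistical Analysis Plan 8/21/24" and is in the past tense from its first sentence, "Data were analyzed using SPSS Version 29 (IBM, 2023"). Its last paragraph explains a choice of method by the data in hand: "With only two timepoints we could not conduct formal analyses of mediation". The protocol had planned three assessments (section 10, Measures): baseline, then "4 months after baseline (Termination or T2), and 12 months after baseline (T3").

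Protocol section 9 lists one primary endpoint, self-harm. The five secondary endpoints are depression, family functioning, alcohol/substance use, emotional dysregulation and risky sexual behaviors. On analysis, the protocol text says only that the study statistician will analyze the data (section 12).

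The SAP's analyses of outcomes and mechanisms are:

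- Mixed ANOVAs of change by treatment condition, using "the Total scores from the PHQ-9, the Difficulty with Emotion Regulation Scale and the Family Connectedness Scale".
- A between-arm test of suicidal thoughts: "Chi-Square Tests of Association were used to determine whether the proportion of youth endorsing thoughts of suicide differed by treatment condition".
- Chi-square tests of change over time in whether youth could talk to a parent: "This analysis was conducted by condition examining mothers and fathers separately".
- Hierarchical logistic regressions in the full sample, relating four proposed mechanisms to past-month self-harm at termination, adjusted for gender and LGBTQ status.
- Descriptive rates of self-harm and suicidal thoughts by condition at baseline and termination.
- A look at change in youth in the clinical range at baseline, and a Reliable Change Index for depression. The number of tests, if any, is not stated for either.

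The only numeric thresholds given are for effect size: "cutoffs for partial eta-squared effect sizes are small .01, moderate .06, large .14".

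**The concern.** A statistical analysis plan normally shows that outcomes and tests were fixed before the results were known. This one cannot show that, because it was written once the analyses were done and no earlier statement of methods appears. It also gives no order of importance among its tests.

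Aim 2 in protocol section 3 is to investigate preliminary efficacy in reducing self-harm against treatment as usual. The SAP plans no between-arm test or estimate of an effect on self-harm. In the same part of the document, suicidal thoughts, a related but unlisted outcome, does get a between-arm test. A significant result on that outcome, or on any one secondary outcome, could be presented as the trial's efficacy finding, and nothing in the documents would tell a reader how much weight it can bear.

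**Working it through.** **1. Endpoints against analyses.**

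| Section 9 endpoint | Analysis in the SAP |
|---|---|
| Self-harm (primary) | Descriptive by arm; also the outcome in full-sample mechanism models whose listed terms do not include treatment arm |
| Depression | Mixed ANOVA (PHQ-9), between-arm |
| Family functioning | Mixed ANOVA on family connectedness, between-arm; plausibly the measure of this endpoint, but the protocol text does not name the instrument |
| Alcohol/substance use | None |
| Emotional dysregulation | Mixed ANOVA, between-arm |
| Risky sexual behaviors | None |
| Not listed: suicidal thoughts | Chi-square, between-arm |
| Not listed by name: talking to a parent | Chi-square over time within each condition; may be a facet of family functioning |

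The assessment at 12 months (T3) is not used in any analysis.

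**2. Counting the tests.**

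- Mixed ANOVAs: 3, each comparing change between arms.
- Suicidal thoughts: at least 1, between arms.
- Talking to a parent: 2 conditions × 2 parents = 4, within arm.
- Mechanism regressions: 4 if each mechanism has its own model, full sample.

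The total is 3 + 1 + 4 + 4 = 12. Of these, 3 + 1 = 4 compare the arms, and the other 8 do not.

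**3. Error rate for the between-arm tests.** The documents give no error rate to reproduce, and no significance level or sidedness. Two-sided α = 0.05 per test is an assumption.

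- Independent tests: 1 − (1 − α)^k. With k = 4, 1 − 0.95^4 = 1 − 0.8145 = 0.1855, or 18.5%.
- Correlated tests: simulation with equally correlated normal test statistics, 300,000 draws, at least one |z| > 1.96, k = 4.

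| Pairwise correlation | Chance of at least one false positive |
|---|---|
| 0 | 18.5% |
| 0.3 | 17.4% |
| 0.5 | 15.5% |
| 0.7 | 13.2% |

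If the clinical-range analysis adds one between-arm test, k = 5 and the independent figure is 1 − 0.95^5 = 0.2262, or 22.6%.

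These figures cover only the number of tests. If outcomes were selected after results were seen, that would add an amount that cannot be computed from the documents.

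**The case against.** The case for the plan is substantial. The trial claims only preliminary efficacy in 100 adolescents, and the SAP describes its mechanism work as exploring patterns. Running several tests without formal adjustment is acceptable in such a trial, provided they are labelled exploratory. Requiring a particular adjustment would be a matter of preference. That stands, and the fix below does not require one.

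Four stronger readings are tempting, and the documents do not support them.

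- *The outcomes and tests were chosen after unblinding.* The past tense dates the writing, not the choices. Depression, emotion dysregulation and family functioning were named in protocol section 9, and an earlier unposted plan may exist.
- *The plan tests outcomes outside the protocol.* Three of the four between-arm tests map to listed secondary endpoints, one of them (family connectedness) plausibly rather than by name. Only suicidal thoughts is clearly unlisted. Talking to a parent is uncertain because the instruments are not visible.
- *The plan tests at an unadjusted 5%.* No significance level appears anywhere, so 5% is the reviewer's assumption.
- *The error rate is 46%.* That is 1 − 0.95^12 = 0.460, taken over all 12 tests as if independent. Eight of them are within-arm changes or full-sample associations and do not compare treatments. Independence is also doubtful, since protocol section 4 says these problems cluster.

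What remains is the absence of any shown pre-specification, hierarchy or exploratory label for the between-arm tests, and the lack of a between-arm analysis of the primary endpoint.

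**Conclusion.** The concern holds in a limited form. On the documents, the SAP's p-values cannot be read as pre-planned evidence of efficacy. The error inflation over the four between-arm tests is moderate: roughly 13% to 19% against a nominal 5%, assuming two-sided 0.05 per test, no adjustment, and pairwise correlation between 0.7 and 0. The larger weakness is one of content: the primary endpoint has no between-arm test or effect estimate, and two secondary endpoints and the 12-month assessment are not analysed. A reader might infer that the analyses were selected for their results. The documents neither show that nor rule it out.

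**What to change.** 1. State at the head of the SAP that it was written after the data were analysed, or cite the earlier plan and its date.
2. Report results in section 9 order. Put self-harm first, with a between-arm estimate and confidence interval. The past-month binary variable at termination, already used in the mechanism models, would serve.
3. Say which endpoints and time points were not analysed, naming substance use, risky sexual behaviors and T3.
4. Mark suicidal thoughts as post hoc. Do the same for talking to a parent, unless it belongs to the family-functioning measure.
5. Label all tests exploratory, give estimates with intervals, and make no efficacy claim from any single nominal p-value.

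Holm-adjusted p-values for the between-arm tests may be shown beside the nominal ones. With four tests at an assumed 0.05, the first step is 0.05/4 = 0.0125. Adjustment of this kind does not repair post hoc selection of outcomes.

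The cost is a short addition to the SAP and report and one further analysis of a variable already in use. The downside is less favourable conclusions.
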